#### 8.2.2. Electrocardiograms

Single 12-lead ECG will be obtained as outlined in the SoA (see Section 1.3) using an ECG machine that automatically calculates the heart rate and measures PR, RR, QRS, QT, and QTcF

intervals. Refer to Section 7.1. of the Master Protocol CPMP for QTcF withdrawal criteria and any additional QTcF readings that may be necessary.

Additional details related to ECG are provided in the Master Protocol CPMP.

### **8.2.3. Clinical Safety Laboratory Tests**

See BP05 Section 10.2 (Appendix 2) for the list of clinical laboratory tests to be performed and to the SoA for the timing and frequency for ISA BP05.

Additional details are provided in the Master Protocol CPMP.

## **8.3. Adverse Events, Serious Adverse Events, and Product Complaints**

The definitions of AEs, SAEs, and PCs can be found in Appendix 3 of the Master Protocol CPMP.

See the Master Protocol CPMP Section 8.3 for additional details.

### **8.3.1. Pregnancy**

#### **Collection of pregnancy information**

##### ***Male participants with partners who become pregnant***

- The investigator will attempt to collect pregnancy information on any male participant's female partner who becomes pregnant while the male participant is in this study. This applies only to male participants who receive study intervention.
- After learning of a pregnancy in the female partner of a study participant, the investigator
  - will obtain a consent to release information from the pregnant female partner directly, and
  - within 24 hours after obtaining this consent will record pregnancy information on the appropriate form and submit it to the sponsor.

The female partner will also be followed to determine the outcome of the pregnancy. Information on the status of the mother and child will be forwarded to the sponsor. Generally, the follow-up will be no longer than 6 to 8 weeks following the estimated delivery date. Any termination of the pregnancy will be reported regardless of gestational age, fetal status (presence or absence of anomalies) or indication for the procedure.

##### ***Female participants who become pregnant***

- The investigator will collect pregnancy information on any female participant who becomes pregnant while participating in this study. The initial information will be recorded on the appropriate form and submitted to the sponsor within 24 hours of learning of a participant's pregnancy.

- The participant will be followed to determine the outcome of the pregnancy. The investigator will collect follow-up information on the participant and the neonate and the information will be forwarded to the sponsor. Generally, follow-up will not be required for longer than 6 to 8 weeks beyond the estimated delivery date. Any termination of pregnancy will be reported, regardless of gestational age, fetal status (presence or absence of anomalies) or indication for the procedure.
- While pregnancy itself is not considered to be an AE or SAE, any pregnancy complication or elective termination of a pregnancy for medical reasons will be reported as an AE or SAE.
- A spontaneous abortion, occurring at <20 weeks gestational age, or still birth, occurring at  $\geq 20$  weeks gestational age, is always considered to be an SAE and will be reported as such.
- Any post-study pregnancy related SAE considered reasonably related to the study intervention by the investigator will be reported to the sponsor as described in the Master Protocol CPMP Section 8.3.1. While the investigator is not obligated to actively seek this information in former study participants, they may learn of an SAE through spontaneous reporting.
- Any female participant who becomes pregnant while participating in the study will discontinue study intervention and continue directly to the follow-up phase. The follow-up on the pregnancy outcome should continue independent of intervention or study discontinuation.

### **8.3.2. Hypersensitivity Reactions**

Many drugs, including oral agents and biologic agents, carry the risk of systemic hypersensitivity reactions. If such a reaction occurs, additional data should be provided to the sponsor in the designated CRFs.

Sites should have appropriately trained medical staff and appropriate medical equipment available when study participants are receiving study intervention. It is recommended that participants who experience a systemic hypersensitivity reaction be treated per national and international guidelines.

In the case of a suspected systemic hypersensitivity event, additional blood samples should be collected as described in Section 10.2.1. Laboratory results are provided to the sponsor via the central laboratory.

### **8.3.3. Adverse Events of Special Interest**

Convulsion is an AE of special interest for LY3857210 and will be subject to enhanced surveillance activities. Additionally, convulsion will be analyzed for presentation in the Clinical Study Report in accordance with the SAP.

If a seizure or convulsion is reported, then contact the medical monitor as soon as possible. Additional evaluation or follow-up may be requested.

#### **8.4. Pharmacokinetics**

Blood samples will be collected for measurement of plasma concentrations of LY3857210 as specified in the SoA.

A maximum of 3 samples may be collected at additional time points during the study if warranted and agreed upon between the investigator and the sponsor. The timing of PK samples may be altered during the course of the study based on newly available data to ensure appropriate data collection.

Instructions for the collection and handling of PK samples will be provided by the sponsor.

The date and time (24-hour clock time) will be recorded for

- LY3857210 administration prior to the PK sample collection, and
- PK sample collection.

PK samples may also be used to evaluate safety or efficacy measures related to concerns arising during or after the study.

#### **8.5. Pharmacodynamics**

Pharmacodynamic assessments will not be evaluated in this study.

#### **8.6. Genetics**

See the Master Protocol CPMP for details related to genetic sampling.

[figure not shown]

## 9. Statistical Considerations

The Master Protocol CPMP and CLBP DSA CPMP(2) provide statistical considerations. LY3857210-specific considerations are described here.

### 9.1. Statistical Hypotheses

The Master Protocol CPMP describes the primary hypothesis. CCI

### 9.2. Analyses Sets

The populations are defined in the Master Protocol CPMP.

The PK population includes all randomly assigned participants who received a dose of LY3857210 and have at least 1 evaluable PK sample collected.

### 9.3. Statistical Analyses

If the primary analysis approach needs to be changed, the updated approach will be provided in the SAP and should not lead to modification of this protocol. Any other change to the data analysis methods described, and the justification for making the change, will be described in the SAP and the clinical study report. Additional exploratory analyses of the data will be conducted as deemed appropriate.

The ISA SAP will be finalized prior to unblinding, and it will include more technical and detailed descriptions of the statistical analyses described in this section.

#### 9.3.1. General Considerations

The primary and secondary endpoint and analyses have been described in the Master Protocol CPMP.

Any borrowing of placebo or treatment effect information will be specified in the ISA SAP. Secondary and tertiary/exploratory endpoints and analyses are described in the Master Protocol CPMP and CLBP DSA CPMP(2).

Handling of missing, unused, and spurious data is addressed prospectively in the overall statistical methods described in the protocol and in the SAP, where appropriate. Adjustments to the planned analyses are described in the final CSR.

#### 9.3.2. Tertiary Analysis

Exploratory analyses may be described in the ISA SAP.

### 9.3.3. Safety Analyses

Safety analyses have been described in the Master Protocol CPMP. Additional ISA-specific safety analyses may be described in the ISA SAP.

### 9.3.4. Exploratory Pharmacokinetic Analyses

Plasma concentrations for LY3857210 will be reported graphically and descriptively. Model-based PK and exposure-response relationships for various efficacy and safety measures may be conducted.

## 9.4. Interim Analysis

An interim analysis may be conducted for internal decision making. The potential reasons for interim analyses could include futility analyses, early efficacy analyses, safety analyses, PK analyses or other analyses needed for key business decisions and planning. Unblinding details would be specified in the unblinding plan section of the SAP or in a separate unblinding document. The SAP will describe any interim analyses in greater detail should they occur.

## 9.5. Sample Size Determination

Up to approximately 125 participants will be randomly assigned to LY3857210 and placebo. It is expected that approximately 80% of participants will complete the double-blind treatment period of the study. **CCI**

**CCI**

**CCI**

If there is no treatment

difference between placebo and LY3857210, the probability of meeting the primary objective specified above (that is, false positive) is  $\leq 0.05$ .

## **10. Supporting Documentation and Operational Considerations**

[figure not shown]
### **10.1. Appendix 1: Regulatory, Ethical, and Study Oversight Considerations**

See the Master Protocol CPMP for regulatory, ethical, and study oversight considerations.

## 10.2. Appendix 2: Clinical Laboratory Tests

The Master Protocol CPMP describes tests that may be performed at additional times noted in the SoA for this ISA. This table describes tests unique for ISA BP05.

Other Tests	Assayed by Lilly-designated laboratory
LY3857210 concentration	Results will not be provided to the investigative sites

### 10.2.1. Laboratory Samples to be Obtained at the Time of a Systemic Hypersensitivity Event

#### Purpose of collecting samples after a systemic hypersensitivity event

The samples listed in this appendix are not collected for acute study participant management. The sponsor will use the laboratory tests results from these samples to characterize hypersensitivity events across the clinical development program.

#### When to collect samples after a systemic hypersensitivity event occurs

Collect the samples listed below if a systemic hypersensitivity event is suspected. The timing should be as designated in the table, assuming the participant has been stabilized.

Obtain follow-up pre-dose samples at the next regularly scheduled laboratory sample collection (ideally prior to the next dose after the event) to assess post-event return-to-baseline values.

Timing	Laboratory Test a
Collect from 30 minutes to 4 hours after the start of the event.	total tryptase
• Note: The optimal collection time is from 1 to 2 hours after the start of event.	complements (C3, C3a, and C5a)
	cytokine panel (IL-6, IL-1 $\beta$ , IL-10 or any cytokine panel that includes these 3 cytokines)

Abbreviation: IL = interleukin.

a All samples for hypersensitivity testing will be assayed by Lilly-designated laboratory. Results will not be provided to the study site. If samples are not collected or are collected outside the specified time period, this will not be considered a protocol deviation.

#### What information to record

Record the date and time when the samples are collected.

**Allowed additional testing for participant management**

The investigator may perform additional tests locally, if clinically indicated, for acute study participant management.

**10.3. Appendix 3: Adverse Events and Serious Adverse Events: Definitions and Procedures for Recording, Evaluating, Follow-up, and Reporting**

See the Master Protocol Appendix 3 for information related to AE and SAE.

## 10.4. Appendix 4: Contraceptive and Barrier Guidance

### 10.4.1. Definitions

Word/Phrase	Definition
Women of childbearing potential (WOCBP)	Adult females are considered WOCBP unless they are WNOCBP.
Women not of childbearing potential (WNOCBP)	
Females are considered WNOCBP if they
 
 
have a congenital anomaly such as Müllerian agenesis
 
are infertile due to surgical sterilization, or
 
are postmenopausal.
 
 
Examples of surgical sterilization include total hysterectomy, bilateral salpingo-oophorectomy, bilateral salpingectomy, or bilateral oophorectomy.

Postmenopausal state	
The postmenopausal state is defined as a woman:
 
 
at any age at least 6 weeks post-surgical bilateral oophorectomy with or without hysterectomy, confirmed by operative note; or
 
aged at least 40 years and up to 55 years with an intact uterus, not on hormone therapya, who has had cessation of menses for at least 12 consecutive months without an alternative medical cause, AND with a follicle-stimulating hormone >40 mIU/mL; or
 
55 years or older not on hormone therapy, who has had at least 12 months of spontaneous amenorrhea, or
 
aged at least 55 years with a diagnosis of menopause prior to starting hormone replacement therapy.
 
 
a Women should not be taking medications during amenorrhea such as oral contraceptives, hormones, gonadotropin-releasing hormone, anti-estrogens, selective estrogen receptor modulators (SERMs), or chemotherapy that could induce transient amenorrhea.

#### 10.4.2. Contraception Guidance

WOCBP who are completely abstinent as their preferred and usual lifestyle, or in a same-sex relationship as their preferred and usual lifestyle:

Must...	Must not...
agree to either remain abstinent or stay in a same-sex relationship without sexual relationships with males	
 
use periodic abstinence methods 
 
calendar
 
ovulation
 
symptothermal, or
 
post-ovulation
 
 
 
declare abstinence just for the duration of a trial, or
 
use the withdrawal method
 

WOCBP who are NOT completely abstinent as their preferred and usual lifestyle, or NOT in a same-sex relationship as their preferred and usual lifestyle, must do the following:

Topic	Condition
Pregnancy testing	Have a negative serum test result at screening followed by a negative urine result within 24 hours prior to treatment exposure. See the Master Protocol CPMP and the BP05 Schedule of Activities for subsequent pregnancy testing requirements.
Contraception	
Agree to use 1 highly effective method of contraception, or a combination of 2 effective methods of contraception.
 
These forms of contraception must be used for the duration of the study.

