**Examples of different forms of contraception:**

Methods	Examples
Highly effective contraception (less than 1% failure rate)	
 
• female sterilization
 
• combination oral contraceptive pill
 
• progestin-only contraceptive pill (mini-pill)
 
• implanted contraceptives
 
• injectable contraceptives
 
• contraceptive patch (only women <198 pounds or 90 kg)
 
• total abstinence
 
• vasectomy (if only sexual partner)
 
• fallopian tube implants (if confirmed by hysterosalpingogram)
 
• combined contraceptive vaginal ring, or
 
• intrauterine devices
 

Effective contraception	
 
• male or female condoms with spermicide
 
• diaphragms with spermicide or cervical sponges
 
• barrier method with use of a spermicide 
 
○ condom with spermicide
 
○ diaphragm with spermicide, or
 
○ female condom with spermicide
 
 
 

Ineffective forms of contraception whether used alone or in any combination	
 
• spermicide alone
 
• periodic abstinence
 
• fertility awareness (calendar method, temperature method, cervical mucus, or symptothermal)
 
• withdrawal
 
• postcoital douche, or
 
• lactational amenorrhea
 

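### Section 10.4.2 bars abstinence declared only for the trial in one table, but its methods list lets women who are not usually abstinent qualify that way

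*Protocol*

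**What the plan says.** Inclusion criterion 2075 (Protocol Section 5.1) refers sites to Section 10.4 for contraception requirements, so the wording there bears on who may enter the trial. Section 10.4.2 contains two tables for WOCBP, followed by a table of methods.

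- **First table.** It covers "WOCBP who are completely abstinent as their preferred and usual lifestyle", and on the same terms women in a same-sex relationship. They must agree to stay so. The column of things they must not do has three items: periodic abstinence methods, "declare abstinence just for the duration of a trial, or", and withdrawal.
- **Second table.** Its heading is "WOCBP who are NOT completely abstinent as their preferred and usual lifestyle, or NOT in a same-sex relationship as their preferred and usual lifestyle, must" meet the conditions that follow. These are pregnancy testing and contraception. On contraception the woman must "Agree to use 1 highly effective method of contraception, or a combination of 2 effective methods of contraception", and "These forms of contraception must be used for the duration of the study".
- **Methods table.** The top row is labelled "Highly effective contraception (less than 1% failure rate" and has 11 entries. One of them is "total abstinence", with nothing added. The contraceptive patch, vasectomy and fallopian tube implants each carry a condition in the same row. The row of ineffective methods includes periodic abstinence and withdrawal, but does not mention abstinence adopted only for the trial.

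The SAP does not touch on this subject.

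**The concern.** A rule against declaring abstinence only for a trial is aimed at a woman who is not ordinarily abstinent and offers to become so while she takes part. By the section's own sorting, that woman belongs in the second table. The rule is not printed there, and the methods list that goes with that table offers an entry that fits her. The rule stands instead in the table for women who are abstinent, or in a same-sex relationship, as a settled way of life, where it has little effect.

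What is at stake is consistent eligibility and the chance of a pregnancy during treatment. The protocol treats such exposure as something to avoid: criterion 2079 excludes pregnant women, and Section 8.3.1 has a participant who becomes pregnant stop study intervention and move to follow-up. A site that reads Section 10.4.2 by its evident purpose could turn this woman away, and a site that reads it line by line could enrol her.

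**Working it through.** No arithmetic beyond counting applies. The check follows one woman through the text: a WOCBP who is not usually abstinent and proposes abstinence for the study as her only method.

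| Step | Text that governs | Result |
|---|---|---|
| 1. Which table covers her? | Second-table heading: "WOCBP who are NOT completely abstinent as their preferred and usual lifestyle" | The second table |
| 2. What must she do? | Contraception row, second table | One highly effective method, or two effective methods together |
| 3. For how long? | Same row | The study only |
| 4. What counts as highly effective? | Methods table, top row | 11 entries, including total abstinence without a condition |
| 5. Does her table bar trial-only abstinence? | Second table | No; the bar is printed only in the first table |
| 6. Is she eligible on contraception? | Steps 1 to 5 | Yes, on the written words |

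Two comparisons show that the gap is specific to this entry.

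- **Items the first table disallows.** There are three. Two of them, periodic abstinence and withdrawal, reappear in the methods table as ineffective, so the tables agree on those. The third, trial-only abstinence, does not reappear, and the broader term stands among the highly effective methods.
- **Conditions in the highly effective row.** Three of the 11 entries carry one and 11 − 3 = 8 do not. Of those eight, total abstinence is the only one that Section 10.4.2 restricts elsewhere. Where the authors wanted a limit on a method, they could and did write it beside the entry.

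Next, does any other wording close the route? Criterion 2075 adds that contraceptive use should follow local regulations, which may settle the matter in some places but not by this protocol. Section 10.4.2 cites the Master Protocol only for later pregnancy testing, not for which methods count. Nothing else in the two documents confines the abstinence entry to women who are usually abstinent.

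Last, which safeguards remain for her? The second table requires a negative serum pregnancy test at screening and a negative urine test in the 24 hours before first exposure. The Schedule of Activities repeats the pre-dose urine test at Visit 3 for all WOCBP. These keep a woman who is already known to be pregnant from being dosed. Urine tests at Visits 4 to 7 (Weeks 2, 4, 6 and 8) can detect a pregnancy that starts during the 8-week treatment period, but cannot prevent it.

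**The case against.** The strongest reply is that the rule and the entry are addressed to different women. The bar on trial-only abstinence is printed only for women who are usually abstinent or in a same-sex relationship, so it does not bind the woman traced above. A reader might infer that the two tables return literally opposite eligibility answers for the same woman. The documents do not support that: one table speaks and the other is silent. What remains is a conflict of purpose, visible when the tables are read together.

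A second reply is that the methods table is a general list of examples sorted by effectiveness. On that view the two group headings decide who may rely on abstinence, and the entry only contrasts total with periodic abstinence. The second heading also joins its conditions with an *or*. Read literally, that sends a usually abstinent woman who is not in a same-sex relationship into the second table, which might explain the entry. This reading is possible, but it does not confine the entry to such women. It also leaves the list without a clear use for the first group, whose table does not ask them to choose a method.

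Two further inferences go too far. One is that urine testing after dosing is the only protection left; the serum test at screening and the urine test before dosing also apply. The other is that the woman would be using no contraception. The methods table itself classes total abstinence as highly effective, so the accurate statement is that she would use no method other than abstinence. Whether trial-only abstinence is adequate is a clinical question that these documents do not settle.

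Finally, Section 5 requires the eligibility criteria of the Master Protocol and the disease-state addendum to be followed. Neither is available here, and either might add limiting wording. That sites would in fact decide differently is a possibility the text allows, not something shown.

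**Conclusion.** The point holds as a gap between two tables of the same section. As written, a WOCBP who is not usually abstinent can meet the contraception condition by abstaining for the trial only, with no other method. That is the conduct the first table disallows, so eligibility under criterion 2075 can be read two ways.

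The size cannot be stated as a number. The documents do not say how many WOCBP are expected or how many would name abstinence as their method. No endpoint, analysis, error rate or sample-size figure depends on it. The consequence is limited to eligibility decisions and possible pregnancy exposure during treatment.

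The conclusion assumes that the methods table is what sites use to decide what counts as highly effective, since it is the only such list in the documents, and that the Master Protocol and the addendum do not already resolve the matter. It does not assume that the bar ought to cover the second group.

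**What to change.** Reconcile the total abstinence entry in the methods table with the rule on trial-only abstinence in the first table, so that Section 10.4.2 gives a single answer for WOCBP who are not usually abstinent. The sponsor decides which statement governs and for which group. Check the result against any contraception wording in the Master Protocol and the addendum.

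The cost is a short wording change in Appendix 4. It adds no visit, test or procedure and leaves the statistical plan untouched.
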